7.6 Procedures for monitoring patient compliance

In accordance with standard clinical practice the treating physician or designee will assess compliance of CZP or other RA treatments at each contact with the patient. The information will be recorded in the observational form.

7.7 Concomitant medication(s)/treatment(s)

7.7.1 Permitted concomitant treatments (medications and therapies)

The treating physician is free to add, withdraw, or alter doses of any kind of medication at his/her own discretion based on standard medical practice and according to the marketing authorization. Refer to the treatment label for adequate prescription.

All concomitant medication and treatment must be recorded in the appropriate study documents (ie, observational form and source data).

The patient should be asked at each visit on new vaccinations received.

8 RECOMMENDED STUDY PROCEDURES BY VISIT

The schedule and the procedures of the study visit are recommended in accordance with the current clinical practice in this patient population. Data should be collected from a visit at the time nearest to that described in the schedule below.

8.1 Visit 1 (Week 0) Screening and/or Baseline

Prior to any study-specific activities, patients will be asked to read, sign, and date a data consent form. Patients will be given adequate time to consider any information concerning the study, given to them by the treating physician or designee. Patients will be prescribed antirheumatoid arthritis medication at the discretion of the treating physician.

The following data should be collected (if part of physicians' routine clinical practice):

- Demographics/medical history (including prior medical procedures related to RA)
- Presence of anti-cyclic citrullinated peptide antibodies (ACPA) or relevant rheumatic auto-antibodies
- RA history
- Prior and concomitant medication (including prior vaccinations)
- Drug administration
- Joint scores (28 count TJC, SJC)
- CRP or ESR
- Morning stiffness
- Physician's global assessment of disease activity using a VAS

Confidential Page 22 of 89

- Patient's assessments
 - Patient's global assessment of disease activity using a VAS
 - Arthritis pain VAS
 - Fatigue Assessment Scale
 - HAQ-DI
 - EQ-5D
- Collect information on sick leave
- Employment status and employability due to RA

8.2 Visit 2 to Visit 9 (Week 6 to Week 104)

A patient may be enrolled into the study after the start of CZP treatment if he/she met all inclusion and exclusion criteria at the start of CZP treatment. Written data consent must be obtained no later than the start of Visit 2 and prior to conducting any clinical assessment at Visit 2. Following written data consent (ie, enrollment into the study), all relevant data from original records will be entered onto study-specific forms.

The following data should be collected (if part of physicians` routine clinical practice):

- Concomitant medication (including vaccinations)
- Concomitant medical procedures
- Adverse events
- Drug administration
- Joint scores (28-count TJC, SJC)
- CRP or ESR
- Morning stiffness
- Physician's global assessment of disease activity using a VAS
- Patient's assessments
 - Patient's global assessment of disease activity using a VAS
 - Arthritis pain VAS
 - Fatigue Assessment Scale
 - HAQ-DI
 - EQ-5D
- Collect information on sick leave
- Employment status and employability due to RA

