5.2 Schedule of study assessments

The schedule of study assessments by visit are presented below.

Assessments ^a	Treatment period ^b							Safety Follow -Up		
Visit	V1	V2	V3	V4	V5	V6	V7	V8	V9	V10
Week	0	6	12	24	36	52	64	76	104	116
Written Data Consent ^c	X	X								
Demographics / Medical History	X									
Presence of Rheumatoid Factor	X									
Presence of anti-cyclic citrullinated peptide antibodies	X									
RA history	X									
Concomitant Medication	X	X	X	X	X	X	X	X	X	X
Adverse Events		X	X	X	X	X	X	X	X	X
Drug administration	X	X	X	X	X	X	X	X	X	
Joint scores (TJC, SJC) (28 joint count)	X	X	X	X	X	X	X	X	X	
Acute phase reactant (CRP or ESR)	X	X	X	X	X	X	X	X	X	
Morning stiffness	X	X	X	X	X	X	X	X	X	
Patient's Global Assessment of Disease Activity (VAS)	X	X	X	X	X	X	X	X	X	
Physician's Global Assessment of Disease Activity (VAS)	X	X	X	X	X	X	X	X	X	

Confidential Page 18 of 89

Assessments ^a	Treatment period ^b							Safety Follow -Up		
Visit	V1	V2	V3	V4	V5	V6	V7	V8	V9	V10
Week	0	6	12	24	36	52	64	76	104	116
Arthritis pain VAS	X	X	X	X	X	X	X	X	X	
Fatigue Assessment Scale	X	X	X	X	X	X	X	X	X	
HAQ-DI	X	X	X	X	X	X	X	X	X	
EQ-5D	X	X	X	X	X	X	X	X	X	
Sick leave	X	X	X	X	X	X	X	X	X	
Employment status and employability due to RA	X	X	X	X	X	X	X	X	X	
Information on subsequent RA treatment										X

CRP=c-reactive protein; EQ-5D=Euro Quality of Life – 5Dimensions; ESR= erythrocyte sedimentation rate; HAQ-DI; Health Assessment Questionnaire-Disability Index; RA=rheumatoid arthritis; SJC=swollen joint count; TCJ=tender joint count; V=Visit; VAS=Visual Analogue Scale

Confidential Page 19 of 89

^a Only if assessed as per current clinical practice. Since this is a noninterventional study, no additional diagnostic or monitoring procedure will be applied.

b Visits are recommended to be quarterly.

Written data consent will be obtained before any data are collected on study-specific forms. Written data consent may be obtained after the start of CZP treatment if the patient met all inclusion and exclusion criteria at the start of CZP treatment. For these patients, written data consent must be obtained at the start of Visit 2 and prior to conducting any clinical assessment at this visit.

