6.3 Withdrawal criteria

Patients are free to withdraw from the study at any time without prejudice to their continued care.

If a patient discontinues for any reason, this reason must be recorded on the Study Completion Form. The physician will be encouraged to invite the patients who discontinue CZP therapy early to return to the clinic/practice for posttreatment. A Safety Follow-Up Visit will be performed 84 days after administration of the last dose of CZP.

In case a patient withdraws his/her data consent no further data should be collected or submitted on this patient or caregiver. If a patient is institutionalized, this should be recorded on the medical update form. Follow-up of hospitalized patients should continue during hospitalization. Hospitalization, by itself, does not necessarily constitute a reason for discontinuation.

The treating physician is free to add or withdraw any kind of medication, or to withdraw the patient from the study at his/her own discretion.

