8.3 Safety Follow-Up Visit (Week 116)

At Week 116 (or 84 days after the last treatment in the case of withdrawal), the following data should be collected (if part of physicians` routine clinical practice):

- Concomitant medication
- Adverse events
- Current RA treatment

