10 ASSESSMENT OF SAFETY

10.1 Adverse events

10.1.1 Definition of adverse event

An AE is any untoward medical occurrence in a patient or clinical investigation patient administered a pharmaceutical product which does not necessarily have a causal relationship with this treatment. An AE can therefore be any unfavorable and unintended sign (including an abnormal laboratory finding), symptom, or disease temporally associated with the use of a medicinal (investigational) product, whether or not related to the medicinal (investigational) product.

Patients will be assessed at all study visits including the Withdrawal Visit (if applicable) and at the Safety Follow-Up Visit 84 days after last dose of study medication. This includes all AEs not present prior to the initial visit and all AEs which recurred or worsened after the initial visit.

Signs or symptoms of the condition/disease for which the investigational product is being studied should be recorded as AEs only if their nature changes considerably or their frequency or intensity increases in a clinically significant manner as compared to the clinical profile known to the treating physician from the patient's history or the Baseline Period.

Confidential Page 26 of 89

Changes in scales and questionnaires will not be assessed as AEs.

Medical procedures will not be assessed as AEs; however, the reason for the procedure may be assessed as an AE.

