10.1.2 Procedures for reporting and recording adverse events

The patient will be given the opportunity to report AEs spontaneously. A general prompt will also be given at each study visit to detect AEs, for example:

"Did you notice anything unusual about your health (since your last visit)?"

In addition, the treating physician should review any self-assessment procedures (eg, questionnaires) that are employed in the study.

If an SAE is reported, UCB must be informed within 24 hours of receipt of this information by the site (see contact details for SAE reporting). The treating physician must forward to UCB (or its representative) a duly completed Adverse Event Report form provided by UCB, even if the data are incomplete or if it is obvious that more data will be needed in order to draw any conclusions. Information recorded on this form will be entered into the global safety database.

If clarifications on the AE are necessary, UCB shall request additional information from the treating physician. He/she shall provide the requested information within a timely manner (maximum 7 calendar days) to allow accurate and timely reporting to the concerned regulatory authorities when applicable.

The Adverse Event Report form must be provided in English, all other requested information can be provided in German.

Additional information (eg, autopsy or laboratory reports) received by the treating physician must be provided within 24 hours. All documents in the local language must be accompanied by a translation in English, or the relevant information included in the same document must be summarized in the Adverse Event Report form. Translations into English will be done by the local Drug Safety department of UCB.

UCB has to perform an assessment of all AEs regarding seriousness and company causality. In case UCB upgrades a case to serious (death, life threatening, medically important event, hospitalization, significant/persistent disability, congenital anomaly), the physician will be informed. UCB also assesses a company causal relationship to CZP, independent of the physician's causal relationship.

The treating physician is specifically requested to collect and report to UCB (or its representative) any AEs, and to also inform participating patients of the need to inform the treating physician of any AE during the study.

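### Adverse event collection is conditional on routine practice in Sections 8.2, 8.3 and the schedule footnote but unconditional in Sections 10.1.1 and 10.1.2, with no rule on which prevails

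*Protocol*

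**What the plan says.** Three places make the collection of adverse events depend on what the physician ordinarily does:

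- Section 8.2 (Visits 2 to 9): "The following data should be collected (if part of physicians` routine clinical practice". Adverse events are an item in the list that follows.
- Section 8.3 (Week 116, or 84 days after last treatment on withdrawal): "the following data should be collected (if part of physicians` routine clinical practice". The list has three items, and adverse events are one of them.
- Section 5.2, footnote a: "Only if assessed as per current clinical practice. Since this is a noninterventional study, no additional diagnostic or monitoring procedure will be applied". The footnote mark sits on the column header for all assessments, so it reaches the adverse event row and the Visit 10 column.

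The safety section sets no such condition:

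- Section 10.1.1: "Patients will be assessed at all study visits including the Withdrawal Visit (if applicable) and at the Safety Follow-Up Visit". The next sentence makes clear that this concerns adverse events.
- Section 10.1.2: "A general prompt will also be given at each study visit to detect AEs", and "The treating physician is specifically requested to collect and report to UCB (or its representative) any AEs".
- Section 10.4 requires 24-hour reporting of serious events, suspected transmission of an infectious agent and events of interest.

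Section 4.2 names the incidence of adverse events as the single safety variable. Section 12.1 defines the Safety Set by one dose of study drug and nothing more. Section 12.4.1 summarises adverse events descriptively on that set.

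**The concern.** The two sets of instructions cannot both be met at a site where asking about adverse events is not routine. Section 8 lets such a site leave the item out, while Section 10.1.2 requires the prompt. About 160 sites are planned, and staff working from the visit lists may act differently from staff working from the safety section.

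What is at stake is the ascertainment of the study's only safety variable. If nobody asks at a visit, nonserious events that the patient does not volunteer may never enter the data, and no later analysis rule can recover them. Serious events and events of interest are better protected, because the 24-hour duty applies whatever the visit lists say.

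**Working it through.** The plan gives no figure for adverse event ascertainment. Its one sample-size figure concerns the remission rate and is reproduced here only for completeness: n = z² × p(1 − p) / d² = 1.95996² × 0.25 / 0.03² = 1067.07, rounded up to 1068, as stated in Section 12.7. It has no bearing on this point, which is settled by setting the texts side by side.

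1. **Does the condition reach adverse events?** Yes, on a literal reading. In 8.2 and 8.3 the condition stands in the lead-in and adverse events are a bullet beneath it, with no exception. In 5.2 the words "Only if assessed as per current clinical practice" attach to the header over every row.

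2. **Is the safety section conditional?** No. Sections 10.1.1, 10.1.2 and 10.4 contain no reference to routine practice.

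3. **Is there a rule of precedence?** No. Section 13.5 requires every item of the protocol to be followed exactly, which applies equally to both sets of text. The title of Section 8 calls its procedures recommended, which hints that Section 10 is the stronger text, but nothing says so.

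4. **Does the noninterventional design require the condition?** Footnote a gives its reason as avoiding added diagnostic or monitoring procedures. That suits joint counts, CRP and similar assessments. A spoken question about health is hard to place in that class, and Section 10.1.2 demands it in this same study. According to the log of Amendment 3, the request to collect and report any adverse event was added to match the sponsor's current template for noninterventional studies. The sponsor therefore treats unconditional collection as compatible with this design.

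5. **Illustration only, resting on an assumption.** Let q be the share of patients never asked at any visit and with no event recorded by any other route. The documents give no value for q. If all dosed patients form the denominator, observed incidence = true incidence × (1 − q). For a true incidence of 20%:
   - q = 10%: 0.20 × 0.90 = 18.0%
   - q = 20%: 0.20 × 0.80 = 16.0%
   - q = 30%: 0.20 × 0.70 = 14.0%
   - q = 40%: 0.20 × 0.60 = 12.0%

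   The relative loss equals q by construction, so this shows the mechanism and not its size.

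**The case against.** The strongest reply is that a sensible reader would let Section 10 govern. It is the dedicated safety section, whereas Section 8 uses one generic lead-in for all its visit lists. Section 13.5 means that omitting the prompt breaches 10.1.2 whatever Section 8 says, so a site could not claim full compliance. Footnote a's own rationale arguably does not extend to asking about events. Spontaneous reports, the 24-hour duties and monitoring against source records (Sections 11.1 and 11.1.2) would also catch part of what a missed prompt loses. All of this stands. It limits the consequence but does not remove the conflict, because the visit lists and schedule still say something different.

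Three stronger readings are tempting, and the documents do not support them:

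- *That the Safety Follow-Up Visit itself is optional.* Section 8.3 conditions the data gathered there, not the visit. For patients who discontinue, Section 6.3 says "A Safety Follow-Up Visit will be performed 84 days after administration of the last dose of CZP", although it also only encourages physicians to invite early discontinuers back.
- *That unasked patients are counted as free of events by rule.* No section says so. It is an inference from the Safety Set definition combined with crude incidence. Section 12.5 leaves missing data to the statistical analysis plan, which is not at hand and may set another denominator.
- *That the under-count has a known size.* Any percentage only restates the assumed q. It also supposes that whole patients go unasked throughout, with nothing captured by other routes.

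**Conclusion.** The contradiction is real, can be read directly from the current text, and should be corrected. Its likely effect is uneven ascertainment across sites and under-ascertainment of incidence, mainly for nonserious events. The direction is a reasoned expectation. The size cannot be computed from the documents. The conclusion assumes that at least some sites would work from the visit lists or the schedule and do not ask about adverse events as routine. If every site follows Section 10, no events are lost and only the wording is at fault. The point belongs in the protocol because it concerns what is collected, which an analysis plan cannot repair.

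**What to change.** Reconcile the passages. In footnote a of Section 5.2 and in the lead-ins of Sections 8.2 and 8.3, state that adverse events are exempt from the routine-practice condition and are collected as set out in Sections 10.1.1 and 10.1.2. Leave the condition in place for the clinical assessments.

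A small optional addition is to record the answer to the adverse event prompt (yes or no) at each attended visit, if the observational form, which is not shown, does not already do so. This would separate patients who were not asked from patients who had no event.

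The cost is wording in three places and, if adopted, one field per visit. The downside is a brief enquiry at sites that would not otherwise make one. No diagnostic procedure or extra visit is added.

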8.3 Safety Follow-Up Visit (Week 116)

At Week 116 (or 84 days after the last treatment in the case of withdrawal), the following data should be collected (if part of physicians` routine clinical practice):

- Concomitant medication
- Adverse events
- Current RA treatment

9 ASSESSMENT OF EFFICACY

9.1 Arthritis Assessment

The joint assessment will be carried out on 28 joints. The 28 joints are shoulders, elbows, wrists (includes radiocarpal, carpal, and carpometacarpal bones which are to be considered as a single unit), metacarpophalangeal joints (MCP I, II, III, IV and V), thumb interinterphalangeal (IP) joints, proximal interphalangeals (PIP II, III, IV, and V) joints, and the knees.

Artificial and ankylosed joints are excluded from both tenderness and swelling assessments.

The swelling and the tenderness of each joint are graded on a 2–point scale as set out below:

Present	Swelling Response (28)	Tenderness Response (28)
No	None	Not tender
Yes	Detectable synovial thickening with or without loss of bony contours, or bulging synovial proliferation with or without cystic characteristics	Positive response to questioning (tender) spontaneous response elicited (tender and winced) or withdrawal by subject on examination (tender, winced, and withdrew)

9.2 Arthritis Pain VAS

Patients will rate how much pain they are experiencing at the time of the visit caused by their arthritis (ie, my pain at this time is) (see Appendix 16.1).

9.3 Patient's Global Assessment of Disease Activity Using a VAS

Patients will score their global assessment of their arthritis, in response to the question 'Considering all the ways your arthritis affects you, how are you feeling today?', using a VAS' (see Appendix 16.2).

9.4 Physician's Global Assessment of Disease Activity Using a VAS

The treating physician will assess the overall status of the patient with respect to the RA signs and symptoms and the functional capacity of the patient using a VAS. This assessment

Confidential Page 24 of 89

by the physician must be made blind to the Patient's Global Assessment of Disease Activity (see Appendix 16.3).

9.5 Fatigue assessment scale

Patients will be asked to rate their fatigue during the past week on a numeric scale (see Appendix 16.4).

9.6 CDAI

The CDAI will be calculated using the sum of the tender and swollen joint counts and the Physician's and Patient's Global Assessment of Disease Activity.

The CDAI will not be calculated by the prescribing physician during the course of the study, but will be computed in the database for analysis purposes.

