4.1.2 Secondary efficacy variables

- Change from Baseline in patient's arthritis pain as measured by Patient's Assessment of Arthritis Pain VAS at Visit 9 (around Week 104)
- Change from Baseline in patient's physical function as measured by the HAQ-DI (by Fries et al, 1980 and Lautenschläger et al,1997) at Visit 9 (around Week 104)
- Change from Baseline in disease activity measured by CDAI at Visit 9 (around Week 104)

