9.9 ACR/EULAR remission definition

The ACR and the EULAR suggested a provisional suggestion (Felson et al, 2011) based on a Boolean criterion. At any time point, a patient must satisfy all of the following:

2011 ACR/EULAR remission criteria:

- TJC ≤1
- SJC <1
- $CRP \le 1 mg/dL$
- Patient's Global Assessment of Disease Activity (PtGADA) ≤10mm (on a scale of 0 to 100mm)

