16.3 Physician's Global Assessment of Disease Activity

Physicians will be asked to assess the overall status of the subject's rheumatoid arthritis signs and symptoms and the functional capacity of the subject using a 100 mm Visual Analogue Scale (VAS) between 0 (Very Good) and 100 (Very Poor).

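### Section 9.6 sums two 0–100 global assessments with two 28-joint counts and states no conversion, so the CDAI as written runs 0–256 and 78% of that range comes from the VAS scores

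*Protocol*

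**What the plan says.** Protocol section 4.1.2 lists three secondary efficacy variables, one of which is "Change from Baseline in disease activity measured by CDAI at Visit 9 (around Week 104"). Section 4.1.3 adds the change in CDAI by visit.

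The score is defined in section 9.6: "The CDAI will be calculated using the sum of the tender and swollen joint counts"; the two global assessments, one by the physician and one by the patient, are the remaining terms. The same section says that the physician does not calculate it and that it is derived in the database for analysis.

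The components are fixed elsewhere in the protocol:

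- **Joint counts (9.1):** "The joint assessment will be carried out on 28 joints", and "The swelling and the tenderness of each joint are graded on a 2–point scale as set out below", that is, present or absent.
- **Physician's global (Appendix 16.3):** a 100 mm VAS "between 0 (Very Good) and 100 (Very Poor").
- **Patient's global (Appendix 16.2):** a line with end points marked 0 and 100. Section 9.9 confirms the unit when it uses the same item for the ACR/EULAR criterion: "on a scale of 0 to 100mm".

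The protocol gives no divisor for the globals, no range or cut-off for the CDAI, and no literature reference for it.

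**The concern.** Section 9.6 does more than list components. It names an operation, a sum, and assigns the calculation to the database. A programmer who takes the four quantities as the protocol defines them would add two counts out of 28 to two readings out of 100. The globals would then carry most of the score's range, and the index would largely report how two VAS readings moved.

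A second programmer, used to globals on 0–10, would divide by 10 first. Both could say they had followed 9.6, and they would report very different values for a secondary endpoint. A reader of the results could not tell from the protocol which scale had been used.

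**Working it through.** The protocol states no CDAI range, SD or target, so there is no figure of its own to reproduce. The check is on the range and on what the two readings do to a change score.

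**Inputs.** Maximum TJC 28 and maximum SJC 28 (9.1). Maximum S of each global: 100 as recorded (9.9, Appendices 16.2 and 16.3), or 10 if each reading is divided by 10 (assumption).

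**Range.** Maximum score = 28 + 28 + 2S. Share of the range from the globals = 2S / (56 + 2S).

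- As written, S = 100: maximum = 56 + 200 = 256; globals 200/256 = 78.1%, joints 56/256 = 21.9%.
- Rescaled, S = 10: maximum = 56 + 20 = 76; globals 20/76 = 26.3%, joints 56/76 = 73.7%.

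**Effect on a change score.** The four patients below are invented for illustration. Each is given as (TJC, SJC, patient global in mm, physician global in mm), Baseline then Visit 9.

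| Patient | As written | Change | From VAS | Each global /10 | Change | From VAS | Ratio of changes |
|---|---|---|---|---|---|---|---|
| A: (8, 6, 60, 50) to (2, 1, 30, 20) | 124 to 53 | −71 | 60/71 = 85% | 25 to 8 | −17 | 6/17 = 35% | 4.2 |
| B: (10, 8, 60, 60) to (2, 1, 20, 20) | 138 to 43 | −95 | 80/95 = 84% | 30 to 7 | −23 | 8/23 = 35% | 4.1 |
| C: (4, 3, 70, 60) to (1, 0, 30, 20) | 137 to 51 | −86 | 80/86 = 93% | 20 to 6 | −14 | 8/14 = 57% | 6.1 |
| D: (20, 15, 50, 50) to (5, 3, 20, 20) | 135 to 48 | −87 | 60/87 = 69% | 45 to 12 | −33 | 6/33 = 18% | 2.6 |

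The two scales do not differ by a constant factor. Patients C and D improve almost equally as written (−86 and −87), but by −14 and −33 after rescaling. A mean change on one scale therefore cannot be converted to the other; the score has to be recomputed from its components.

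**Limit of the check.** A share of the range is not a share of the observed variance. The protocol gives no SDs for the components, so the actual contribution of the globals in this population cannot be computed from it.

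**The case against.** The best defence is that section 9 describes instruments and section 12 leaves statistical detail to the SAP, which is not at hand. Section 9.8 treats the DAS28 in the same way, giving components only and a calculation in the database. Section 9.6 says sum but does not tell anyone to add raw millimetres, and it does not forbid rescaling. Score derivation is ordinary SAP content. All components are scheduled at Visits 1 to 9, so the divisor can be set at analysis without losing data. The variable is analysed descriptively, with no test or decision attached.

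Much of this stands, and it limits the severity. It does not remove the point. Section 9.8 lists what goes into the DAS28 and prescribes no operation; 9.6 prescribes one, and with the protocol's own scales that operation gives 0–256. An SAP that divides by 10 would be adding a step that the protocol's definition lacks. Section 9.9 shows that this protocol does state the scale when it uses the patient's global in another composite.

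A reader might go further and infer that the score in 9.6 is not the CDAI at all. The document cannot show that, because it gives no reference definition or range for the index. The 0–10 globals and the 0–76 range come from outside convention and are used here only as a labelled assumption.

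**Conclusion.** The point holds as a scaling gap in a secondary endpoint. Read with the protocol's own scales, section 9.6 gives a score of 0–256 with 78% of the range from the two VAS scores; with each global on 0–10 it gives 0–76 and 26%. The first pair of figures rests on protocol text alone. The second rests on the assumption that the conventional scale is intended.

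It should be fixed, but it is not critical. The primary variable is DAS28 remission and the sample size rests on the precision of that remission rate; neither uses the CDAI.

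Two further inferences are tempting and are not supported:

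- **Joint exclusion.** Section 9.1 says "Artificial and ankylosed joints are excluded from both tenderness and swelling assessments". A reader might conclude that such joints score 0 and bias the CDAI and DAS28 downward. The section does not say that they score 0, the protocol gives no frequency for them, and a rule for non-assessable joints is ordinary SAP content. The weighting sentence shown in Amendment 2 is superseded text, and its removal is not itself an error. Prorating is only one of several options.
- **Duplication.** A reader might say that the unscaled score nearly repeats other VAS results. Neither global is listed as an efficacy variable of its own in 4.1.2 or 4.1.3, pain is not a component of the CDAI, and the protocol gives no correlations.

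**What to change.** In section 9.6 replace the verbal definition with:

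CDAI = TJC28 + SJC28 + (patient global in mm)/10 + (physician global in mm)/10, range 0–76.

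The SAP should carry the same line. Any interim table that already shows the CDAI should be checked for the scale it used and recomputed from the components if necessary.

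The cost is one formula line. All four components are already in the assessment schedule, so no new data, form or visit is needed.
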